10.6. Protection of data: National Data Processing Commission “CNIL”

In accordance with law No. 78-17 of 6 January 1978 on Data Processing, Data Files and Civil Liberties, amended by law 2004-801 of 6 August 2004 concerning the protection of individuals with regard to the processing of personal data, this protocol will be subject to a declaration of compliance with a reference method to the French Data Protection Agency (CNIL).

Taking into account the fact that the study comes within the scope of MR003, the compliance commitment of Pfizer allows us to start without the opinion of the French Data Protection Agency (CNIL).

10.7. Ethical conduct of the study

The study will be conducted in conformity with legal and juridical requirements, as well as the objective, value and scientific rigor and in compliance with generally accepted practices of research described in recommendations on pharmacoepidemiologic good practice (GPP) published by the International Society for Pharmacoepidemiology (ISPE), recommendations of good epidemiological practice (GEP) published by the International Epidemiological Association (IEA), good practice of research on results published by the International Society for Pharmacoeconomics and Outcomes Research (ISPOR), the international ethical recommendations for epidemiological research published by the Council for International Organizations of Medical Sciences (CIOMS), the European network of pharmacoepidemiology and pharmacovigilance centres (ENCePP) of the European Medicines Agency (EMA), the guide of methodological standards in pharmacoepidemiology and FDA guidelines for industry: Good Pharmacovigilance and Pharmacoepidemiologic Assessment, FDA guidelines for industry and for FDA staff: Good Practice of Conduct and Reporting of Pharmacoepidemiologic Safety Studies using all electronic medical data, and guide lines for industry: measures of change noted by the patient; use in development of medicinal products in support of labelling and/or equivalent.

11. MANAGEMENT AND REPORTING OF ADVERSE EVENTS

11.1. Single reference document on safety of use

The current French Summary of Product Characteristics (SmPC) will be the single reference safety document during the study. It will be used by Pfizer pharmacovigilance department to evaluate any safety event reported to the Pfizer pharmacovigilance department by the investigator during this study.

This single safety reference document should be used by the investigator for prescribing information and recommendations.

11.2. Requirements in terms of pharmacovigilance

The following table summarises the requirements for recording of adverse events in the electronic case report and for reporting adverse events via the Adverse Event Reporting Form for noninterventional studies to Pfizer pharmacovigilance (NIS AEM Report Form). These requirements are defined by three types of events:

- (1) serious adverse events (SAE)
- (2) non-serious adverse events (AE) (if applicable), and
- (3) situations involving exposure to a medicinal product including exposure in pregnancy, exposure in a breastfeeding mother, medicinal product errors, overdoses, misuse, extravasation and occupational-related exposure.

These events are defined in the section entitled “Definition of an adverse event”.

	Recorded in the study electronic CRF	Reported via NIS AEM Report Form to Pfizer Pharmacovigilance within 24H following the awareness of the event
SAE	All	All
Non-serious AE	All	
Potential risk (RMP XELJANZ in force) :
 
 - Malignancy - Cardiovascular risk - Gastrointestinal perforation - Interstitial lung disease - Progressive multifocal leukoencephalopathy - Increased immunosuppression when used in combination with biologic DMARDs and immunosuppressants including B lymphocyte depleting agents - Increased risk of adverse events when tofacitinib is administered in combination with MTX - Primary viral infection following live vaccination - Increased exposure to tofacitinib when co-administered with CYP3A4 and CYP2C19 inhibitors - Off-label use including children with JIA - Higher incidence and severity of adverse events in the elderly
Situations involving exposure to a study medicinal product including exposure in pregnancy, exposure in a breastfeeding mother, medicinal product errors, an overdose, misuse, extravasation, lack of efficacy and occupational exposure	All (independently of existence of a concomitant AE), except for occupational exposure	All (independently of existence of a concomitant AE)

For each AE, the participating physician must look for and obtain sufficient information, both in order to determine the outcome of the adverse event and to evaluate if it satisfies criteria for classification as an SAE (see section entitled “serious adverse events” below).

Adverse events must be reported to Pfizer within 24 hours following awareness of the event by the participating physician, whether the event has been considered as related to the study medicinal product or not by the participating physician.

In particular, if a serious adverse event is fatal or life-threatening, reporting to Pfizer must be done immediately, whatever the information available on the adverse event. This time period also applies to all new information (follow-up) relating to reporting of adverse events forwarded previously. In rare cases where the participating physician is not immediately informed of occurrence of an adverse event, the participating physician must report the event within 24 hours after he becomes aware of it and complete the information at time when he became aware of this adverse event for the first time.

For adverse events considered as serious or identified in the right-hand column of the abovementioned table which are to be reported to Pfizer within 24 hours following awareness of them, the participating physician is required to look for and to provide all further information to Pfizer in conformity with this 24h time period. Furthermore, Pfizer can request that a participating physician obtain in an urgent manner specific further information on follow-up. This information can be more detailed than that recorded in the study case report form. Generally, this information will include a sufficiently detailed description of the adverse event in order to enable complete medical evaluation of the case and the independent determination of a possible causal relationship. All relevant information regarding the event, such as concomitant treatments or disorders, must be provided. If a patient dies, a summary of available results of an autopsy must be forwarded as soon as possible to Pfizer or to its certified representative.

Period of reporting

For each patient, the period of reporting of adverse events starts from the time the patient received the first dose of the study medicinal product or from the date on which the patient provided his/her informed consent if he/she has previously been exposed to the study medicinal products, and ends at end of the study period of observation which should include at least a period of 28 calendar days after the last administration of the study medicinal product; a report must be sent to the PFIZER Pharmacovigilance department or to its certified representative for all types of adverse events listed in the abovementioned table and occurring during this period. If the patient receives the study medicinal product on last day of the observational period, the reporting period will be extended by 28 calendar days after the end of the observational period.

In the event that the patient provides his/her consent but was never enrolled in the study (for example, the patient changed his/her mind on participation; failure in terms of screening criteria), the period of reporting ends on date of decision for non-inclusion of the patient.

If the participating physician becomes aware of a serious adverse event which occurred at any time after the end of the observational period, and he/she considers it related to a study medicinal product, this serious adverse event must also be reported to the Pfizer Pharmacovigilance department.

Evaluation of causal relationship

The participating physician must evaluate and record the causal relationship. For all adverse events, sufficient information must be obtained by the participating physician in order to determine the causal relation of each adverse event. For AE considered as related to a study medicinal product, the participating physician is required to perform follow-up up until resolution or stabilisation of the event and/or of its sequelae at a level considered acceptable by the participating doctor and that Pfizer is in agreement with this evaluation.

Evaluation of the causal relationship by the participating physician is the determination of the fact that a reasonable possibility exists that a study medicinal product has caused or has contributed to an adverse event. If the final determination of a causal relation is “unknown” and that the participating physician cannot determine if a study medicinal product has caused an event, then the event must be reported within 24 hours.

If the participating physician cannot determine the aetiology of the event but that he/she has determined that no study medicinal product was the cause of the event, information on this must be clearly provided in the case report form and in the adverse event reporting form for noninterventional studies.

Definition of an adverse event

Adverse events

An adverse event is any untoward medical occurrence in a patient or clinical investigation subject administered a pharmaceutical product and which does not necessarily have a causal relationship with this treatment. It is not necessary that the event have a causal relationship with the treatment or use. Examples of adverse events include, without this list being exhaustive, the following:

- a. Abnormal test results (see the following for circumstances in which an abnormal test result constitutes an AE);
- b. Clinically significant symptoms and signs;
- c. Changes to results of the clinical examination;
- d. Hypersensitivity; lack of efficacy; abuse of a medicinal product;
- e. Pharmacodependence.

Furthermore, for medicinal products, they can include resultant signs or symptoms:

- a. Of an overdose;
- b. Of withdrawal;
- c. Of misuse;
- d. Of off-label use (Off-Label of MA);
- e. Of medicinal product interactions;
- f. Of extravasation;
- g. Of exposure during pregnancy;
- h. Of exposure during breastfeeding;
- i. Of a medicinal product error;
- j. Of occupational exposure.

Abnormal test results

Criteria enabling to determine if an abnormal result of an objective test must be reported as an adverse event are as follows:

- The test result is associated with symptoms, and/or
- The test result requires further diagnostic investigations or a medical/surgical intervention, and/or
- The test result leads to a change in dosage or to withdrawal of a patient from the study, to administration of a significant additional concomitant treatment, or to another treatment, and/or
- The test result is considered as an adverse event by the participating doctor or the sponsor.

The simple repetition of an abnormal test result, in the absence of one of the aforementioned conditions, does not constitute an adverse event. All abnormal test results which prove to result from an error do not need to be reported as adverse events.

Serious adverse events

A serious adverse event is defined as any untoward medical occurrence in a patient receiving a medicinal product or a nutritional product, whatever the dose, or using a medical device, and that:

- Causes death;
- Is life-threatening;
- Requires hospitalisation of the patient or results in prolongation of hospitalisation (see below for circumstances in which this does not constitute an adverse event);
- Results in permanent or important disability or incapacity (important deterioration of ability to accomplish actions of daily living);
- Results in a congenital anomaly or a malformation.

Progression of a malignancy during the study (including signs and symptoms of progression) must not be reported as a serious adverse event unless its outcome is fatal during the study or during the period of reporting of adverse events. Hospitalisation due to signs and symptoms of progression of the disease must not be reported as a serious adverse event. If a malignancy has a fatal outcome during the study or during the period of reporting of adverse events, then the event leading to death must be recorded as an adverse event, and as a grade 5 serious adverse event.

An event will be defined as medically important based on medical and scientific judgement. A medically important event may not be immediately life-threatening and/or result in death or hospitalisation. However, if it is established that the event can be life-threatening for the patient and/or require an intervention in order to prevent one of the outcomes stated in the above, the medically important event must be reported as serious.

Events, for example, that enter into this category of medically important events are allergic bronchospasm requiring intensive care in the emergency room (ER) or at home, coagulation disorders, seizures which have not resulted in hospitalisation, or development of pharmacodependence or medicinal product abuse.

Furthermore, all suspected transmission of an infectious agent, pathogenic or not, by a Pfizer product is considered as a serious adverse event. Such event can be suspected by clinical symptoms or test results indicating an infection in a patient exposed to a Pfizer product. The terms “suspicion of transmission” and “transmission” are considered synonymous.

These cases are considered as unexpected and must be managed as serious cases by the Pfizer Pharmacovigilance Department. These cases can also be reported as product defect, if applicable.

Hospitalisation

Hospitalisation is defined as any initial admission to hospital (even for a duration less than 24 hours) into a health institution or any prolongation of an admission.

The admission also includes transfer within the hospital to an intensive care unit ICU (for example, from a psychiatric ward to a medical ward, from a medical ward to a coronary intensive care unit, from a neurology ward to a unit for treatment of tuberculosis).

A visit to the ER is not necessarily a hospitalisation; however, an event which leads to a visit to the ER must be evaluated as medically important.

Hospitalisation in the absence of an adverse event is not an adverse event in itself and does not require reporting. For example, the following reasons for hospitalisation without an AE are not to be reported:

- A social admission (for example, patient does not have a place to sleep)
- Administrative admission (for example, for an annual check-up)
- An optional admission not associated with a triggering AE (for example, for a scheduled cosmetic surgery procedure)
- Hospitalisation for observation in the absence of an AE
- Admission for treatment of a pre-existing condition not associated with development of another AE nor with worsening of a pre-existing disorder (for example, for an assessment following persistence of abnormal laboratory test data existing prior to the treatment)
- Planned admission by the protocol during the clinical study (for example, for a procedure required by the study protocol).

Situations requiring reporting to Pfizer Pharmacovigilance within 24 hours:

Situations involving exposure in pregnancy, exposure during breastfeeding, a medicinal product error, an overdose, misuse, extravasation, lack of efficacy, occupational exposure are described in the following.

Exposure in pregnancy (or exposure in utero)

An exposure during pregnancy occurs if:

A woman becomes pregnant or it turns out that she is pregnant while she is receiving or is exposed to a study medicinal product (for example, environmental exposure) or a woman becomes pregnant or it turns out that she is pregnant after having discontinued or having been exposed to a study medicinal product (maternal exposure);

An example of environmental exposure would be a case involving direct contact with a Pfizer product in a pregnant woman (for example, a nurse reports that she is pregnant and has been exposed to a chemotherapy product).

A man has been exposed, in the setting of treatment or of environmental exposure, to a study medicinal product before or around the period of conception and/or has been exposed during pregnancy of his partner (paternal exposure).

Generally, cases of prospective and retrospective exposure in pregnancy, whatever the source, are to be reported, whether an adverse event is present or not, according to the procedure for reporting serious adverse events.

If a female patient in the study or the partner of a study patient becomes pregnant or it turns out that she is pregnant during treatment of a male patient in the study with the study medicinal product, the participating doctor must report this information to Pfizer, whether an adverse event has occurred or not, by completing the adverse event reporting form for noninterventional studies, as well as the additional form entitled “Exposure during pregnancy”.

Furthermore, information relating to environmental exposure to a medicinal product by a pregnant woman (for example, a female patient reports that she is pregnant and reports that she has been exposed to a cytotoxic product by inhalation or after having accidentally spilled it) must be reported to Pfizer, whether an adverse event has occurred or not, by completing the adverse event report form for noninterventional studies, as well as the additional form “Exposure during pregnancy”.

The information forwarded must include the planned date of term of the pregnancy (see the following for information on term of pregnancy).

Follow-up must be implemented to obtain general information on the pregnancy.

Furthermore, follow-up must be implemented to obtain information on the outcome of the pregnancy for all cases which are the subject of reporting of exposure in pregnancy whose outcome is unknown.

A pregnancy must be followed up to its end or up to termination of the pregnancy (for example, voluntary termination of pregnancy) and Pfizer must be informed of its outcome.

This information will be provided in the setting of follow-up of the initial report of exposure during pregnancy. In case of a birth, the structural integrity of the neonate can be evaluated at time of birth.

In case of a termination of pregnancy, the reason must be specified and, if possible clinically, the structural integrity of the foetus must be evaluated by a visual inspection (at least that the results of tests performed before the procedure have concluded in a congenital anomaly and that these results have been reported).

If the outcome of the pregnancy corresponds to criteria of an SAE (for example, an ectopic pregnancy, a spontaneous abortion, a foetal death in utero, a neonatal death or a congenital anomaly [for a viable baby, an aborted foetus, foetal death in utero or neonatal death]), procedures for reporting of SAE must be followed.

Further information on the outcome of pregnancy which are reported as an SAE are as follows:

A spontaneous abortion which includes a miscarriage and non-expulsion of the foetus;

Neonatal deaths which occur during the month following the childbirth must be reported, whatever the causal relationship, as SAEs. Furthermore, death of a baby after one month of age must be reported as an SAE whenever the participating doctor evaluates the death of the child of a young age as related or possibly related to exposure to the study product.

Further information on exposure in pregnancy can be requested. Follow-up on outcome at time of childbirth will be treated on a case-by-case basis (for example, follow-up in children born before full term, of a young age, in order to identify developmental retardation).

In case of paternal exposure, a form for communication of information intended for pregnant partners will be given to the male patient participating in the study for his partner. It must be documented that this document has been given to the patient participating in the study for transmission to his partner.

Exposure during breastfeeding

Situations of exposure during breastfeeding must be reported independently of existence of a concomitant AE.

A report of exposure during breastfeeding must not be filed with a Pfizer product specifically indicated for use in a pregnant woman (for example, vitamins) administered in agreement with the MA.

However, if a toddler presents an AE associated with administration of such a medicinal product, the AE must be reported as with exposure during breastfeeding.

A medicinal product error

A medicinal product error means any unintentional error in prescribing, dispensing or administration of a medicinal product, which can cause or lead to inappropriate use of a medicinal product or to harm for the patient, even though it is under the control of a health professional, the patient or of a consumer. Such events can be related to professional practice, products, procedure, and to systems in particular; prescribing; transmission of an order; product information, packaging and nomenclature of a product; composition; dispensing; distribution; administration; training in use of the product; monitoring and use.

Medicinal product errors include the following:

Near-accidents involving or not a patient directly (for example, administration by inadvertence or error, which is an accidental use of a product outside of indication of prescription by a healthcare professional or a patient/consumer);

Confusion concerning the name of a product (for example, marketing name and trade name).

The participating doctor must report the following medicinal product errors to Pfizer, independently of existence of an associate AE/SAE:

Medicinal product errors involving exposure of a patient to a product, whether the medicinal product error is accompanied by an adverse event or not.

Medicinal product errors not involving a patient directly (for example, potential medicinal product errors or near-accidents). Whenever a medicinal product error does not involve exposure of a patient to a product, the following minimal criteria constitute a case of medicinal product error:

The notifier is identifiable;

A suspect product;

Medicinal product error.

Overdose, Misuse, Extravasation

Cases of an overdose, misuse and extravasation associated with use of a Pfizer product must be reported to Pfizer by the participating doctor, independently of existence of a concomitant AE/SAE.

Lack of efficacy

Cases of lack of efficacy of a Pfizer product must be reported to Pfizer by the participating physician independently of existence of a concomitant AE/SAE; or indication of a Pfizer product.

Occupational exposure

Cases of occupational exposure to a Pfizer product must be reported to Pfizer by the participating physician, independently of existence of a concomitant AE/SAE.

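### Protocol 11.2 bars non-fatal malignancy progression, and hospitalisation for progression of an unnamed disease, from being classed as serious, against its own seriousness criteria

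*Protocol*

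**What the plan says.** All the protocol text is in Section 11.2.

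- **Seriousness criteria (Serious adverse events).** Among the criteria are danger to life and the following: "Requires hospitalisation of the patient or results in prolongation of hospitalisation". A later paragraph adds that a medically important event which can threaten life, or which needs intervention to prevent a listed outcome, has to be reported as serious.
- **Malignancy progression (same subsection).** "Progression of a malignancy during the study (including signs and symptoms of progression) must not be reported as a serious adverse event". The bar applies "unless its outcome is fatal during the study" or during the adverse event reporting period; a fatal case is to be recorded as a grade 5 serious event.
- **Hospitalisation for progression (same paragraph).** "Hospitalisation due to signs and symptoms of progression of the disease must not be reported as a serious adverse event". The sentence does not say which disease, and it carries no exception of its own.
- **Hospitalisation subsection.** One of the admissions that need not be reported is: "Admission for treatment of a pre-existing condition not associated with development of another AE nor with worsening of a pre-existing disorder".
- **Reporting table.** The row for serious events reads All for recording and All for reporting. The row for non-serious events requires all of them in the eCRF. Those on a list beginning "Potential risk (RMP XELJANZ in force" must also reach pharmacovigilance within 24 hours, and malignancy is the first item on that list.
- **Lack of efficacy subsection.** "Cases of lack of efficacy of a Pfizer product must be reported to Pfizer by the participating physician", whether or not there is an accompanying adverse event.

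SAP 8.2.2.1 summarises adverse events, serious adverse events and non-serious adverse events, following sponsor standards that the documents do not reproduce.

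**The concern.** A site that reads the general criteria and a site that reads the progression paragraph can label the same event differently. The paragraph looks carried over from an oncology setting: it assigns a grade 5, but the protocol defines no grading scale and the study is in rheumatoid arthritis.

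The situation can arise here. Prior cancer is not named among the non-inclusion criteria (Protocol 9.2.2), and cancers are a comorbidity recorded at inclusion (SAP Table 1). Contraindication to the drug is a non-inclusion criterion, but the documents do not list the contraindications, so how many such patients enter is unknown.

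Tolerability is a secondary objective (Protocol 8). The SAP reports serious and non-serious events separately and has no rule to harmonise seriousness across about 100 centres. The serious-event table could therefore depend on which sentence each site followed, for a type of event that the protocol itself lists as a potential risk.

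**Working it through.** There is no figure to reproduce and no arithmetic to do. The check is to take each type of event through the passages and see whether they give one answer.

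| Event | General seriousness criteria | Progression paragraph | Result |
|---|---|---|---|
| Newly occurring malignancy, hospitalised | Serious | Silent; it covers progression only | Consistent: serious |
| Malignancy progression, fatal | Serious | Serious, by its exception | Consistent: serious |
| Malignancy progression, non-fatal, no criterion met | Not serious | Not serious | Consistent: non-serious |
| Malignancy progression, non-fatal, hospitalised or life-threatening | Serious | Not to be reported as serious | **Conflict** |
| Rheumatoid arthritis worsening, hospitalised | Serious | Not to be reported as serious, if the unnamed disease is rheumatoid arthritis | **Unclear** |

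**The conflict.** The paragraph on medically important events sharpens it: a progression that can threaten life falls under an instruction to report it as serious and an instruction not to. Nothing in the subsection says which takes precedence.

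**The unclear case.** The hospitalisation criterion points the reader below for exceptions. The Hospitalisation subsection, whose list is given as examples, does not mention disease progression. Its nearest item exempts an admission for a pre-existing condition only when there is no new adverse event and no worsening, and a hospitalised worsening fails that test. So if the unnamed disease is rheumatoid arthritis, the two subsections pull in opposite directions. If it is the malignancy, this case drops out and only the conflict above remains.

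**What happens to the event.** The bar is on reporting an event as serious, not on reporting it. A malignancy progression labelled non-serious still enters the eCRF. The 24-hour follow-up duty also covers it, since that duty is stated this way: "For adverse events considered as serious or identified in the right-hand column of the abovementioned table". This assumes that the site treats progression as falling under the malignancy entry. Rheumatoid arthritis worsening is not on the risk list. It would reach pharmacovigilance as lack of efficacy if so judged, but that route does not settle whether it is serious.

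**Where it shows.** The event moves between the serious and non-serious tables of SAP 8.2.2.1. The total of all adverse events does not change.

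**The case against.** The strongest reply is that nothing here is contradictory. The text introducing the reporting table says that its event types are defined in the section on the definition of an adverse event, and the progression paragraph belongs to that section. On this view, All in the serious row means all serious events as defined, carve-out included. That stands as far as the table is concerned: a reader might infer that the paragraph contradicts the All entry, but the cross-reference lets the two be read together. It does not remove the clash inside the definition, where an event meeting a seriousness criterion is also barred from the label.

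A reader might also infer that cancer safety data are being withheld from the sponsor. The documents do not support this. Fatal outcomes are expressly serious, new malignancies are not touched, and malignancy events labelled non-serious are still recorded and sent within 24 hours.

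A third inference is that every hospitalised worsening of rheumatoid arthritis is excluded. The hospitalisation sentence stands between two sentences about malignancy, so the malignancy is its most natural subject. The Hospitalisation subsection also points away from the wider reading. What remains is that the term is undefined in a rheumatoid arthritis protocol, so some sites may read it the wider way.

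Finally, safety is descriptive in this study, the primary endpoint is drug survival, and the SAP's events of special interest are herpes zoster and serious infections (SAP 6.2), not malignancy. All of that is correct and limits the weight of the point.

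**Conclusion.** The point holds as an unreconciled seriousness rule. Non-fatal malignancy progression that hospitalises a patient or threatens life has no single classification under Protocol 11.2, and hospitalisation for progression of an undefined disease may have none either. The effect is on seriousness classification in the SAP's tables and on consistency between sites, not on whether events are captured. The primary analysis is unaffected.

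The size cannot be estimated. The documents give no number of patients with prior cancer, no expected count of progressions and no view of the eCRF seriousness fields. It would be tempting to say that all such events vanish from the serious-event table by rule. That does not follow, because the paragraph on medically important events tells sites to report some of the same events as serious.

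The conclusion assumes that sites follow the protocol text as written and that the sponsor standards cited in SAP 8.2.2.1 contain no overriding seriousness derivation. No view is taken on which reporting rule is right.

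**What to change.** **Protocol.** The sponsor should reconcile four parts of Section 11.2: the reporting table, the Serious adverse events subsection, the Hospitalisation subsection and the Lack of efficacy subsection. The revised text should state whether the malignancy-progression paragraph applies in this study, which disease the hospitalisation sentence means, and which instruction takes precedence when an event meets a seriousness criterion and is also a progression.

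**SAP 8.2.2.1.** Add a supplementary table, for example: *Recorded malignancy events and hospitalisations that meet the general seriousness criteria of Protocol 11.2 will be tabulated whatever seriousness label the site assigned, alongside that label.* The main tables keep the reported classification, so this does not prejudge the reconciliation. It shows how far the result depends on which passage a site followed.

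**Cost.** A clarification letter or amendment text, one SAP sentence and one extra table. The count of serious events may rise slightly. The table works only if the eCRF captures hospitalisation and outcome for each event, which the documents do not show. Protocol Section 6 planned the end of data collection for January 2023, so a clarification to sites may come too late to change reporting; the SAP table is still useful because all adverse events are to be recorded.
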